#### 7.1.2. Grading Scale for Prompted Events

The grading scales used in this study to assess prompted events as described below are based on concepts outlined in the Food and Drug Administration (FDA) Center for Biologics Evaluation and Research (CBER) guidelines on toxicity grading scales for adults and adolescent volunteers enrolled in preventive vaccine clinical trials, but have been adapted for applicability to healthy infants.

#### 7.1.2.1. Local Reactions

For the first 7 days following each vaccination from Day 1 through Day 7, the subject's legally acceptable representative will be asked to assess redness, swelling, and pain at the injection site and to record the symptoms in the e-diary in the evening. Redness and swelling will be measured and recorded in measuring device units (range: 1 to >14; an entry in the e-diary of 15 will denote >14), and then categorized during analysis as mild, moderate, or severe based on the grading scale in Table 1 below. Measuring device units can be converted to centimeters according to the following scale: 1 measuring device unit = 0.5 cm. Pain at the vaccine injection site will be assessed by the subject's legally acceptable representative as mild, moderate, or severe according to the grading scale in Table 1 below. The subject's legally acceptable representative will be prompted to contact the investigator if the subject experiences a severe (Grade 3 or above) local reaction to assess the reaction and perform an unscheduled assessment or visit as appropriate.

Only an investigator is able to classify a subject's local reaction as Grade 4, after physical examination of the subject or documentation from another medically qualified source (eg, emergency room or hospital record). If a subject experiences a Grade 4 local reaction, the investigator must immediately notify the sponsor. Site staff will educate the subject's legally acceptable representative regarding signs and symptoms that would prompt site contact.

The procedure for notification of the sponsor is provided in the study reference manual (SRM) or equivalent.

Table 1.	Grading	Scales for	or Local	Reactions

	Mild	Moderate	Severe	
	Grade 1	Grade 2	Grade 3 a	Grade 4b
Redness	1 to 4 caliper units	5 to 14 caliper units	>14 caliper units	Necrosis or exfoliative
(synonymous with	(or measuring device	(or measuring device	(or measuring device	dermatitis
erythema)	units)	units)	units)	
	=	=	=	
	0.5 to 2.0 cm	>2.0 to 7.0 cm	>7 cm	
Swelling	1 to 4 caliper units	5 to 14 caliper units	>14 caliper units	Necrosis
(synonymous with	(or measuring device	(or measuring device	(or measuring device	
edema)	units)	units)	units)	
	=	=	=	
	0.5 to 2.0 cm	>2.0 to 7.0 cm	>7 cm	
Pain at injection site	Hurts if gently touched	Hurts if gently	Causes limitation of	Emergency room visit
(tenderness)	(eg, whimpers, winces,	touched, with crying	limb movement	or hospitalization for
	protests, or withdraws)			severe pain
				(tenderness) at
				injection site

Abbreviations: CRF = case report form; e-diary = electronic diary.

Note: If the size of the redness and/or swelling falls between 2 measuring device units, the higher measuring device unit number will be recorded in the e-diary.

- a. Legally acceptable representatives of the subjects experiencing local reactions >14 caliper units (>7.0 cm) are to be contacted by the study site. An unscheduled visit may be required.
- b. Grade 4 assessment should be made by the investigator. Grade 4 will not be collected in the e-diary but as an AE on the CRF. The severity of the local reaction should be graded using the AE severity grading scale in Section 8.3.

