### 6.8. Unscheduled Visits

If the subject's legally acceptable representative reports redness or swelling at the injection site measuring >14 measuring device units (>7 cm) or severe injection site pain or a fever >104.0°F (>40.0°C) during the 7-day postvaccination period, a telephone contact must occur as soon as possible between the investigator or medically qualified designee and subject to assess if an unscheduled investigator site visit is required. Note that for a fever >104.0°F (>40.0°C), the subject's legally acceptable representative should be instructed not to delay seeking medical care, as appropriate, while arranging for an unscheduled visit. An investigator site visit should be scheduled as soon as possible to assess the extent of the reaction unless any of the following is true:

- The subject's legally acceptable representative is unable to bring the subject to the unscheduled visit.
- The reaction is no longer present at the time of the telephone contact.
- The subject's legally acceptable representative recorded an incorrect value in the e-diary (confirmation of an e-diary data entry error).
- The principal investigator (PI) or authorized designee determined it was not needed.

This telephone contact will be recorded in the subject's source documentation and the CRF.

If the subject's legally acceptable representative is unable to bring the subject to an unscheduled visit, or the PI or authorized designee determined it was not needed, any ongoing reactions must be assessed at the next study visit.

During the investigator site visit, the reactions should be assessed by the investigator or a medically qualified member of the study staff such as a study physician or a study nurse, as applicable to the investigator's local practice, who will:

- Measure rectal temperature (°F/°C).
- Measure minimum and maximum diameters of redness (if present).
- Measure minimum and maximum diameters of swelling (if present).
- Assess injection site pain in accordance with the grades provided in Section 7.1.2 (if present).
- Assess for other findings associated with the reaction and record on the AE page of the CRF, if appropriate.

The investigator or an authorized designee will complete the unscheduled visit assessment page of the CRF.

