#### 7.1.1. Subject Electronic Diary

The subject's legally acceptable representative will be asked to monitor and record local reactions, specific systemic events, and antipyretics/pain medication taken for 7 days, each evening following each vaccination using an e-diary (in a provisioned device or application on a personal device), which allows recording of these assessments only within a fixed time window, thus providing the accurate representation of the subject's experience at that time. Data on local reactions, specific systemic events, and antipyretics/pain medication reported in the e-diary will be transferred electronically to the e-diary vendor, where they will be available for review by investigators, their qualified designees, and sponsor staff at all times via an internet-based portal. At intervals agreed to by the vendor and Pfizer, these data will be transferred electronically to Pfizer for analysis and reporting.

The daily e-diary data will not be captured in the CRF. However, if a subject withdraws because of prompted events reported in the e-diary, the event(s) should be recorded on the AE page of the CRF, regardless of whether the investigator considers the event(s) to be clinically significant.

The investigator or designee must obtain stop dates for any reactions ongoing on the last day that the e-diary was completed. The stop dates should be entered in the CRF.

Investigators (or an appropriately qualified designee) are required to review the e-diary data online at frequent intervals (daily is optimal) to evaluate subject compliance and reported events as part of the ongoing safety review.

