## 8.3. Severity Assessment

GRADE	If required on the AE page of the CRF, the investigator will use the adjectives MILD, MODERATE, or SEVERE to describe the maximum intensity of the AE. For purposes of consistency, these intensity grades are defined as follows:	
1	MILD	Does not interfere with subject's usual function.
2	MODERATE	Interferes to some extent with subject's usual function.
3	SEVERE	Interferes significantly with subject's usual function.

Note the distinction between the severity and the seriousness of an AE. A severe event is not necessarily an SAE. For example, a headache may be severe (interferes significantly with the subject's usual function) but would not be classified as serious unless it met one of the criteria for SAEs, listed above.

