# 9.4. Safety Analysis

All safety analyses will be performed using the safety population.

Descriptive statistics for local reactions and systemic events from Day 1 to Day 7 will be presented by severity and cumulatively across severity levels. Descriptive statistics will include proportions of subjects with the indicated endpoint and the associated Clopper-Pearson 95% CIs. Vaccine groups will be compiled separately.

Descriptive statistics for local reactions and systemic events will be compiled separately for each dose. The same descriptive statistics will be compiled across all 4 doses.

AEs (including nonserious AEs, SAEs, and NDCMCs) will be compiled over 2 intervals: from Dose 1 to 1 month following Dose 3 and from Dose 4 to 1 month following Dose 4. SAEs and NDCMCs will be summarized from Dose 1 until 6 months after Dose 4. The descriptive statistics for AEs will be summarized as the number and percentage of subjects reporting at least 1 event of each preferred term with the associated Clopper-Pearson 95% CIs, arranged by system organ class.

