3.1. Primary Endpoints

- Proportions of subjects reporting prompted local reactions (redness, swelling, and pain at the injection site) within 7 days of each dose.
- Proportions of subjects reporting prompted systemic events (fever, decreased appetite, irritability, and drowsiness/increased sleep) within 7 days of each dose.
- Proportions of subjects reporting adverse events (AEs) from Dose 1 to 1 month after Dose 3, and from Dose 4 to 1 month after Dose 4.
- Proportions of subjects reporting serious adverse events (SAEs) and newly diagnosed chronic medical conditions (NDCMCs) from Dose 1 to 6 months after Dose 4.

CCI

Redness and swelling will be measured and recorded in measuring device units (range: 1 to >14; an entry in the e-diary of 15 will denote >14), and then categorized during analysis as mild, moderate, or severe based on the grading scale in Table 4 below. Measuring device units can be converted to centimeters according to the following scale:

1 measuring device unit = 0.5 cm. Pain at the vaccine injection site will be assessed by the subject as mild, moderate, or severe according to the grading scale in Table 4.

Table 4. Grading Scales for Local Reactions

	Mild Grade 1	Moderate Grade 2	Severe Grade 3	Grade 4
Redness (synonymous with erythema)	1 to 4 caliper units (or measuring device units) = >0.0 to 2.0 cm	5 to 14 caliper units (or measuring device units) = >2.0 to 7.0 cm	>14 caliper units (or measuring device units) = >7 cm	Necrosis or exfoliative dermatitis
Swelling (synonymous with edema)	1 to 4 caliper units (or measuring device units) = >0.0 to 2.0 cm	5 to 14 caliper units (or measuring device units) = >2.0 to 7.0 cm	>14 caliper units (or measuring device units) = >7 cm	Necrosis
Pain at injection site (tenderness)	Hurts if gently touched (eg, whimpers, winces, protests, or withdraws)	Hurts if gently touched, with crying	Causes limitation of limb movement	Emergency room visit or hospitalization for severe pain (tenderness) at injection site

Note: If the size of the redness and/or swelling falls between 2 measuring device units, the higher measuring device unit number will be recorded in the e-diary.

Note: Grade 4 assessment should be made by the investigator. Grade 4 will not be collected in the e-diary but as an AE on the CRF.

For each local reaction, the maximum severity grade will be derived for the e-diary collection period (Day 1 to Day 7, where Day 1 is the day of each vaccination) as follows:

= missing and =0, CCI

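### Does a Grade 4 redness or swelling drop out of sight because the diary grades by size and the AE page by function?

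*Protocol*

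**What the plan says.** Protocol 7.1.2.1 has the caregiver record redness and swelling in measuring-device units, "and then categorized during analysis as mild, moderate, or severe based on the grading scale in Table 1 below". SAP 3.1 says the same of its own table: "and then categorized during analysis as mild, moderate, or severe based on the grading scale in Table 4 below". In both tables Grades 1 to 3 for these two reactions are size bands. Grade 4 is a tissue finding: for redness "Necrosis or exfoliative dermatitis", for swelling necrosis alone.

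Grade 4 is reserved to the investigator and is not entered in the diary. Footnote b to Protocol Table 1 makes it an AE on the CRF and adds: "The severity of the local reaction should be graded using the AE severity grading scale in Section 8.3". Section 8.3 has three levels set by effect on function. The lowest reads "Does not interfere with subject's usual function" and the highest is severe.

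On analysis, Protocol 9.4 states: "Descriptive statistics for local reactions and systemic events from Day 1 to Day 7 will be presented by severity and cumulatively across severity levels". SAP 6.1.1.1 summarizes local reactions by maximum severity, which SAP 3.1 derives over the diary period. AEs are tabulated by preferred term and system organ class.

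**The concern.** The three scales do not map onto each other. Size decides the row in the reaction table, tissue damage decides Grade 4, and function decides the AE intensity. A confirmed Grade 4 redness of 2.0 cm or less that leaves the infant's function unaffected is therefore mild by size and mild by Section 8.3. No visible sentence carries the investigator's Grade 4 into the severity table.

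In a study whose primary objective is to describe safety, that would put the top grade of the protocol's own scale in one of its lowest rows. A reader who looked only at that table could conclude that an arm had nothing worse than mild or moderate redness.

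**Working it through.** The plan gives no figure on this point, so the check is mainly a comparison of the texts, with one illustration.

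**1. Size bands.** One unit is 0.5 cm. Codes 1 to 4 reach 4 × 0.5 = 2.0 cm (mild). Codes 5 to 14 run from 2.5 cm to 14 × 0.5 = 7.0 cm (moderate). Code 15 means more than 7 cm (severe). A necrotic lesion can fall in any band, so a Grade 4 case can be tabulated below severe.

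**2. Other graded events.** The mismatch with Section 8.3 is not confined to redness and swelling.

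| Event | Grade 4 in Protocol Tables 1 and 2 | Sent to Section 8.3 by | Already severe by definition? |
|---|---|---|---|
| Redness, swelling | Tissue finding | Table 1 footnote b | No |
| Pain | Emergency visit or admission for severe pain | Table 1 footnote b | Yes |
| Decreased appetite, drowsiness, irritability | Emergency visit or admission for the severe symptom | Table 2 footnote a | Yes |

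All six graded events have a Grade 4 that a three-level scale cannot express. Fever is grouped by temperature and has no Grade 4. Only for redness and swelling can the diary row fall below severe without contradicting the Grade 4 definition.

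**3. Where the event is counted.** AEs are a primary endpoint over two intervals: Dose 1 to 1 month after Dose 3, and Dose 4 to 1 month after Dose 4. Together they contain the 7-day window after each of the four doses. A Grade 4 reaction with onset in a diary window is therefore in an AE table. That table is arranged by preferred term, not by Section 8.3 intensity, so a mild intensity rating does not remove the event or move it to another row. Protocol 8.1.1 asks for concise medical terms. For an unscheduled visit Protocol 6.8 adds: "Assess for other findings associated with the reaction and record on the AE page of the CRF, if appropriate". Since Grade 4 redness or swelling is itself a named lesion, its AE term would probably identify it. That is an assumption about coding.

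**4. Size of the effect.** The documents give no Grade 4 rate and none is assumed. Take one case with a diary size of 7.0 cm or less, no other severe case, and the planned 230 infants per arm. The Clopper-Pearson 95% limits are:

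- 0/230: lower limit 0; upper limit 1 − 0.025^(1/230) = 0.0159, or 1.59%.
- 1/230 = 0.43%: lower limit 1 − 0.975^(1/230) = 0.00011, or 0.01%; upper limit, the 0.975 quantile of Beta(2, 229), is 0.0240, or 2.40%.

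The two intervals overlap almost entirely.

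**5. What a change would do.** Stating where the label is kept, and footnoting the reaction table with a Grade 4 count, leaves the diary data as they are. The severe-or-worse entry would still read 0/230 (0 to 1.59%). Only merging investigator diagnoses into caregiver measurements would alter it, and that would mix two kinds of observation in one severity scale.

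**The case for a change.** The strongest case for acting is that the primary endpoint is displayed by severity and the visible derivation cannot produce the top grade. SAP Table 4 keeps a Grade 4 column without saying what fills it, and omits the protocol's sentence about Section 8.3. A footnote and perhaps one CRF item would cost almost nothing. The AE tables also pool Doses 1 to 3, so they do not show which of those doses preceded the event.

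Part of this stands. In the visible text neither document says where the Grade 4 classification is stored or shown, and the wording of the footnotes could be tighter.

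The rest is weaker. The SAP 3.1 derivation of maximum severity is interrupted by redaction, so the absence of a rule cannot be established. The CRF is not among the documents and may already hold the item. The separation of sources looks deliberate: Protocol 7.1.1 says "The daily e-diary data will not be captured in the CRF", and both documents keep Grade 4 out of the diary. Footnote b is then best read as adding an intensity rating, not as replacing the Grade 4 label. The protocol also prompts the caregiver to call for a Grade 3 or worse local reaction, so one main route to an investigator's examination starts from an entry that is already severe, though other routes exist.

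**Conclusion.** The gap in the visible wording is real but small, and no change to the plan follows. A Grade 4 event is reported to the sponsor immediately, recorded as an AE and counted in a primary endpoint. Clarifying where the label is kept would leave every tabulated proportion and interval as it is. SAP 5.1 rules out hypothesis tests and decision rules, so no inference or sample-size figure depends on the point.

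The most that one case could move is the severe-or-worse figure in one arm, between 0% (0 to 1.59%) and 0.43% (0.01% to 2.40%), and then only if the two data sources were merged. An analyst with a confirmed Grade 4 case in hand would flag it beside the reaction table without needing an amendment.

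This rests on three assumptions: the planned 230 infants per arm as denominator, a positive diary entry for the affected infant (so that the proportion with any reaction is unchanged), and an AE term that names the lesion. If the third failed, the immediate report to the sponsor would still keep the case known.

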#### 7.1.2.2. Systemic Events (Systemic Symptoms and Fever)

## 7.1.2.2.1. Systemic Event Symptoms

For the first 7 days following each vaccination from Day 1 through Day 7, the subject's legally acceptable representative will be asked to assess decreased appetite, drowsiness/increased sleep, and irritability and to record the symptoms in the e-diary (in a provisioned device or application on a personal device) in the evening. The symptoms will be assessed by the subject's legally acceptable representative as mild, moderate, or severe according to the grading scale in Table 2 below. The subject's legally acceptable representative will also be instructed to contact site staff if the subject experiences any possible Grade 4 prompted systemic event (ie, emergency room visit or hospitalization for

severe decreased appetite, severe drowsiness/increased sleep, or severe irritability) within 7 days after vaccination. Study staff may also contact the subject's legally acceptable representative to obtain additional information on Grade 3 events entered into the e-diary.

Only an investigator is able to classify a subject's systemic event as Grade 4, after physical examination of the subject or documentation from another medically qualified source (eg, emergency room or hospital record) or telephone contact with the subject's legally acceptable representative. If a subject experiences a Grade 4 systemic event, the investigator must immediately notify the sponsor.

The procedure for notification of the sponsor is provided in the SRM or equivalent.

Systemic Event	GRADE 1 Mild	GRADE 2 Moderate	GRADE 3 Severe	GRADE 4 a
Decreased appetite (loss of appetite)	Decreased interest in eating	Decreased oral intake	Refusal to feed	Emergency room visit or hospitalization for severe decreased appetite (loss of appetite)
Drowsiness (increased sleep)	Increased or prolonged sleeping bouts	Slightly subdued, interfering with daily activity	Disabling, not interested in usual daily activity	Emergency room visit or hospitalization for severe drowsiness (increased sleep)
Irritability (fussiness) (synonymous with	Easily consolable	Requiring increased attention	Inconsolable; crying cannot be comforted	Emergency room visit or hospitalization for severe irritability (fussiness)

**Table 2.** Grading Scales for Systemic Events

Abbreviations: CRF = case report form; e-diary = electronic diary.

#### 7.1.2.2.2. Fever

restless sleep; decreased sleep)

In order to record information on fever, a digital thermometer will be given to the subject's legally acceptable representative with instructions on how to measure rectal temperature at home. Temperature will be collected in the evening daily for 7 days following vaccination (Days 1 to 7, where Day 1 is the day of vaccination) and at any time during the 7 days that fever is suspected. Fever is defined as a rectal temperature of  $\geq 100.4^{\circ}F$  ( $\geq 38.0^{\circ}C$ ). The highest temperature for each day will be recorded in the e-diary. In the event of a fever on Day 7, temperature will be collected daily until fever has resolved (1 day of temperature less than  $100.4^{\circ}F$  [ $38.0^{\circ}C$ ]) in order to collect a stop date in the CRF. A subject's legally acceptable representative will be prompted to contact the investigator if the subject experiences a fever  $\geq 104.0^{\circ}F$  ( $\geq 40.0^{\circ}C$ ) to assess the fever and perform an unscheduled assessment. Study staff may also contact the subject's legally acceptable representative to

a. Grade 4 assessment should be made by the investigator; Grade 4 will not be collected in the e-diary but will be collected as an AE on the CRF. The severity of the systemic event should be graded using the AE severity grading scale in Section 8.3.

obtain additional information if a temperature of >102°F is entered into an e-diary. Temperature will be measured and recorded to 1 decimal place and then grouped into ranges for the analysis; see Table 3 below.

#### **Table 3.** Ranges for Fever

100.4°F to 101.1°F (38.0°C to 38.4°C)	
101.2°F to 102.0°F (38.5°C to 38.9°C)	
102.1°F to 104.0°F (39.0°C to 40.0°C)	
>104.0°F (>40.0°C)	

[figure not shown]
## 7.1.2.3. Use of Antipyretic/Pain Medication

The subject's legally acceptable representative will be asked to record the use of antipyretic/pain medication (yes/no) in the e-diary (in a provisioned device or application on a personal device) in the evening daily for 7 days after each dose of investigational product.

The use of prophylactic antipyretic/pain medication, while permitted, is not recommended on the day of investigational product administration (before or after vaccination).

